635 636	At the 4-week clinic visit and 8-week clinic visit (if it occurs in clinic), the following also will be done:	
637 638	Height, weight, blood pressure/pulse measured	
639	At 13-week visit, the following also will be done:	
640	Height, weight, blood pressure/pulse measured	

641 • Blood draw for central lab measurement of HbA1c, lipids, creatinine 642 PRO surveys completed 643 5.3 Transition to Pre-study Insulin Therapy 644 At the end of the RCT, study staff will supervise the participant's transition back to their prior 645 therapy. 646 • Study staff will re-evaluate the subject's baseline therapy doses, noting changes in basal rates, carbohydrate ratios, and correction factors in use at the end of the trial. 647 648 • Participants must have two CGM or fingerstick blood glucose values, separated by at 649 least 15 minutes, that are above 80 mg/dL prior to discharge from the clinic. 650 Study staff will confirm subjects have carbohydrates on hand for their drive back home, and instruct subjects to check their glucose levels when they arrive at home, prior to 651 bedtime, and at least one time overnight on the first night to monitor for hypoglycemia, 652 reminding subjects that insulin on board can be active for the next few hours even after 653 stopping the study pump. 654 655 5.3.1 3-Day Post-Study or Discontinuation of AID System Contact 656 Participants will have a post-study contact 3 (±1) days after permanently discontinuing the study AID system and transitioning back to their prior insulin therapy (which for most participants will 657 be at the end of the RCT), during which the following will occur: 658 659 • Check on transition back to usual home diabetes care 660 • Assessment of adverse events 661 5.4 Safety Visits Following Changes in Glucose-Lowering or Weight-**Reduction Medications** 662 663 The only changes of glucose-lowering or weight-reduction medications permitted will be a reduction in dose for safety reasons, or an adjustment to an equivalent dose of a different 664 665 formulation if participant's insurance coverage changes. No increased doses or initiation of a 666 new glucose-lowering or weight-reduction medication will be permitted. 667 If a participant in the AID group has a reduction in dose or requires a change of glucoselowering or weight-reduction medication due to insurance coverage, an unscheduled visit will 668 669 occur after 1-2 days and 7 days to assess safety. 670 **5.5 Early Termination Visit** 671 Participants in the AID group who discontinue use of the AID system will be asked to continue using the study CGM and remain in the study through the 13-week visit. 672 673 In the event of participant withdrawal or early termination in both groups, participants will be 674 asked to come to clinic for an end of study visit. If the visit occurs 4 or more weeks after

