
randomization, the procedures listed for the 13-week visit will be completed (may be combined

with the 4-week visit if in window for the 4-week visit).

Participants in the AID group who discontinue use of the AID system prior to the end of the RCT and have not already resumed their pre-study insulin regimen will be transitioned back to their pre-study insulin regimen as described in section 5.3 and will have a 3-day post-study call.

677

678 679

680

PAGE 47 OF 79

681		Chapter 6: Exercise and Meal Challenges
682		6.1 Overview
683 684 685	challen	ticipants in the AID group will be asked to perform 3 meal challenges and 3 exercise ges unless ineligible due to cardiac or other safety concerns, with the expectation that the y of participants in the AID group will complete all challenges.
686 687 688 689	Participants will be advised that for the exercise challenges, they must have a care partner capable of providing treatment for severe hypoglycemia, including glucagon use, who will be present during and for one hour following each study exercise challenge. Training will be provided by study staff to the care partner as needed.	
690 691 692 693 694	consecu 4 week	timately 25% of each type of challenge (meal or exercise) will be performed on 3 ative days within each of the following 4 periods time from randomization: 1-2 weeks, 3-s, 5-6 weeks, 7-8 weeks. Challenges that cannot be scheduled during these time periods lenges that need to be rescheduled may be performed, if necessary, between weeks 9 and
695 696 697	Participants will be instructed to communicate with study staff within one day prior to each challenge to review procedures and to have a contact with study staff after the completion of each challenge within one day.	
698	6.2 Meal Challenges	
699 700 701	being u	neal challenges will be performed on 3 consecutive days while the study AID system is sed. The same meal should be used for each of the 3 meal challenges—either lunch or (participant choice).
702	The three meal challenges will consist of:	
703	•	No bolus for the meal
704 705		50% bolus – calculate the bolus dose using the bolus calculator and deliver half the recommended dose of insulin.
706	•	Full bolus for the meal based on calculated bolus dose using the bolus calculator.
707	For each meal challenge, participants will:	
708 709		Be in a fasting state for two hours prior to consuming the meal and the last manual insulin bolus more than two hours prior to the meal.

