9.6 Stopping Criteria

9.6.1 Participant Discontinuation of Study Device

- 1202 In the case of an unanticipated system malfunction resulting in a severe hypoglycemia or DKA
- event (or a malfunction that could have led to severe hypoglycemia or DKA), use of closed-loop
- mode will be suspended while the problem is diagnosed. The UADE will be reported to the IRB,
- DSMB, and FDA. After assessment of the problem and any correction, use of closed-loop mode
- will not be restarted until approval is received from the IRB, DSMB, and FDA.
- In the absence of a device malfunction, a participant will be discontinued from the study if any of the following occur:
- The investigator believes it is unsafe for the participant to continue on the intervention.

 This could be due to the development of a new medical condition or worsening of an
- 1210 This could be due to the development of a new medical condition of worsening of an 1211 existing condition; or participant behavior contrary to the indications for use of the
- device that imposes on the participant's safety.
- The participant requests that the treatment be stopped
- Participant pregnancy
- Two distinct episodes of DKA, HHS, or severe hypoglycemia as defined in sections 9.2.3 and 9.2.4, respectively.

1217 1218 1219	Each DKA or severe hypoglycemia event will be reviewed by the Medical Monitor with respect to determination of cause and whether the occurrence of the event can be attributed to use of the study device.
1220 1221 1222 1223 1224 1225	An additional requirement for continued study participation following a single DKA or severe hypoglycemia event will be that (1) the site investigator believes that the event is explainable, unlikely to recur, and that it is safe for the participant to continue to use the system and (2) the Medical Monitor concurs. If the Medical Monitor determines that the occurrence of the event indicates that it is not safe for the participant to continue to use the study system, the participant will be discontinued from the study.
1226 1227	Even if the study device system is discontinued, the participant will be encouraged to remain in the study (using CGM only) through the final study visit.
1220	
1228	9.6.2 Criteria for Suspending or Stopping Overall Study

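### Protocol 9.6.1 takes participants out of the study for device, treatment and acute-event reasons, against its own closing paragraph and section 5.5; the likely effect on 13-week HbA1c is small and the fix is cheap

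*Protocol*

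**What the plan says.** Protocol 9.6.1 is headed Participant Discontinuation of Study Device. Its list begins "In the absence of a device malfunction, a participant will be discontinued from the study if any of the following occur". The items are:

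- the investigator considers the intervention unsafe to continue;
- "The participant requests that the treatment be stopped";
- pregnancy;
- "Two distinct episodes of DKA, HHS, or severe hypoglycemia as defined in sections 9.2.3 and 9.2.4, respectively".

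The section then deals with a single DKA or severe hypoglycemia event. If the Medical Monitor concludes that "it is not safe for the participant to continue to use the study system, the participant will be discontinued from the study".

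The closing paragraph of the same section points the other way: "Even if the study device system is discontinued, the participant will be encouraged to remain in the study", on CGM only, up to the final visit. Protocol 5.5 agrees with that paragraph: "Participants in the AID group who discontinue use of the AID system will be asked to continue" with the study CGM and to stay to week 13.

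For actual withdrawal or early termination, 5.5 asks for an exit visit but sets no deadline for it. "If the visit occurs 4 or more weeks after" randomization, "the procedures listed for the 13-week visit will be completed"; these include the central-lab HbA1c. SAP 5.8 admits HbA1c to the analysis only if it was collected on days 61 to 121. Protocol 11.5 and SAP 6.1 analyse participants as randomized, whatever their device use.

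Protocol 10.7 separately makes pregnancy a study discontinuation, so that item is consistent and is not part of this point.

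**The concern.** Stopping a device and leaving a trial are different events, and 9.6.1 treats them as one. The list and the Medical Monitor sentence are mandatory; the closing paragraph only encourages people to stay. Nothing ranks them. Across the planned 20–25 sites, some could reasonably follow the mandatory text.

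The primary outcome is then at risk. Central-lab HbA1c is scheduled only at randomization and week 13, so a participant removed without a usable exit sample contributes only a baseline value to the direct-likelihood model. With the planned correlation of 0.3, baseline explains 0.3² = 9% of the variance at follow-up, so little is recovered. Most of the triggers concern the intervention or the study system, so the loss would fall mainly on the AID arm and be related to outcome.

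Other losses are partial. CGM metrics need only 168 hours of follow-up data (SAP 5.3), so most leavers still count, without their later readings. Under Protocol 9.2.9, ongoing UADEs and related SAEs are followed after exit, but collection of other adverse events ends.

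**Working it through.** **1. Reproduce the planned power.** Inputs from Protocol 11.3 and SAP 4: SD 1.0, correlation with baseline 0.3, two-sided 5% test, 300 completers. Allocation is 2:1 (Protocol 4.3), giving 200 AID and 100 Control.

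- Residual SD = 1.0 × √(1 − 0.3²) = 0.954
- SE = 0.954 × √(1/200 + 1/100) = 0.1168
- Power = Φ(difference/SE − 1.96): 90.2% at 0.38, 85.0% at 0.35, 80.6% at 0.33

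This matches the stated 90%, 85% and 80%.

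**2. Find which removals leave no analysable exit HbA1c.** Take removal on days 0–90 and an exit visit a fixed lag later. The lag is an assumption, because 5.5 sets no deadline.

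| Lag | No HbA1c called for (visit before day 28) | Drawn but outside the window (visit on days 28–60) | Total of 91 days |
|---|---|---|---|
| 0 days | 28 | 33 | 61 (67%) |
| 7 days | 21 | 33 | 54 (59%) |
| 14 days | 14 | 33 | 47 (52%) |

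So the exit visit is only a partial safety net. These are shares of calendar days, not forecasts of how many people are lost.

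**3. Size the bias and the power loss.** The documents give no trigger rate. Let f be the share of the 220 AID participants who end with no usable HbA1c because of the literal reading. As f is already defined by having no usable value, it is not discounted again by the shares in step 2. Assume f = 1–10%. The 10% end equals the whole planned dropout, so it is an upper bound. Assume also a gap of 0.38 points between those lost and those retained. That is the plan's detectable difference, used here as a yardstick. A 1.0-point gap is shown as a stress case.

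- Bias = f × gap, before any recovery through baseline adjustment
- AID completers = 200 − 220f, Control 100, if the loss comes on top of planned dropout
- Power at 0.38 = Φ(0.38/SE − 1.96), with SE recomputed

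| f | AID lost | Bias, gap 0.38 | In planned SE | Bias, gap 1.0 | AID completers | Power at 0.38 |
|---|---|---|---|---|---|---|
| 0 | 0 | 0 | 0 | 0 | 200 | 90.2% |
| 1% | 2.2 | 0.0038 | 0.03 | 0.010 | 197.8 | 90.1% |
| 2% | 4.4 | 0.0076 | 0.065 | 0.020 | 195.6 | 90.0% |
| 5% | 11 | 0.019 | 0.16 | 0.050 | 189.0 | 89.6% |
| 10% | 22 | 0.038 | 0.33 | 0.10 | 178.0 | 89.0% |

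If these exits fall within the planned 10% dropout, power stays at the planned value and only the bias column applies.

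**4. Allow for voluntary retention.** The fix cannot compel anyone to stay. If half of those affected stay, it recovers about half the bias: 0.5 × 0.0038 = 0.0019 up to 0.5 × 0.038 = 0.019.

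**The case against.** The strongest reply is that the intent is plain. The heading of 9.6.1 is about the device, its last sentence covers this very case, and 5.5 repeats it. Protocol 5.3.1 schedules a contact after permanent device stop and treats that as the end of the RCT only for most participants. Protocol 11.15.1 and SAP 12 count people who stopped AID use separately from the participant flow chart. Harm needs a site to overlook all of this. The 30-person, 6-week pilot (Protocol 1.3) saw no severe hypoglycemia or DKA. SAP 8.4 already plans control-based imputation and a tipping-point analysis.

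Much of that stands. It makes the literal reading less likely and keeps the expected effect small. It does not remove the conflict: the mandatory wording appears twice and nothing subordinates it. The pilot does not support a high event rate, but it says nothing about requests to stop treatment over 13 weeks. The sensitivity analyses probe missing values without recovering them.

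It is also fair to say that the mismatch between the week-4 exit rule and the day 61–121 window affects every early withdrawal. It is the route by which the wording could cost data, not a second fault in 9.6.1.

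Two stronger readings are not supported:

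- A reader might infer that 9.6.1 breaches the intention-to-treat rule. That rule says in which arm people are analysed, and SAP 6.1 keeps everyone with any data. Early exit works against the rule's purpose but does not break it.
- A reader might infer that removing a Control participant after two acute episodes is the same drafting error, since the list is not limited to the AID arm. The texts that contradict the list concern people who stop the device system. For Control, removal may be a deliberate safety choice.

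**Conclusion.** The point holds as a minor drafting contradiction with a cheap remedy. The direct conflict is between the list and Medical Monitor sentence in 9.6.1 on one side, and that section's closing paragraph and 5.5 on the other.

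At an assumed 1–2% of the AID arm lost and a 0.38-point gap, bias is 0.004–0.008 HbA1c points, under 0.07 of the planned SE of 0.117, and power at 0.38 falls by 0.1–0.2 percentage points. At the 10% upper bound, bias is about 0.04 and power about 89%. Bias reaches 0.10 only if both extremes in the table coincide, and nothing in the documents points there.

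A reader might infer a threat to the primary result; these figures do not support that. The loss rate, the gap and the visit lag are all assumptions. The direction of bias is also uncertain: losing people whose treatment failed would flatter AID, while losing people with severe hypoglycemia could work either way.

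**What to change.** Amend Protocol 9.6.1 as follows.

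- **AID participants:** for the three non-pregnancy triggers and the Medical Monitor sentence, change the consequence from leaving the study to *discontinued from use of the AID system*.
- **Pregnancy:** put it on its own line as a study discontinuation, in line with 10.7.
- **Data collection:** add *Unless consent is withdrawn, CGM and adverse event collection continue and HbA1c is drawn at the 13-week visit (days 61–121).*
- **Control participants:** leave the consequence of the triggers to the sponsor and the Medical Monitor, and state it explicitly once they have decided.

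The cost is a short amendment with IRB review. Sample size and analysis do not change.

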9.2.4 Hyperglycemic/Ketotic Events

Hyperglycemia is only reportable as an adverse event when one of the following criteria is met:

- Evaluation or treatment was obtained at a health care provider facility for an acute event involving hyperglycemia or ketosis, or the participant contacted the site and received guidance on how to manage the hyperglycemia/ketosis
- The event involved DKA, as defined by the Diabetes Control and Complications Trial (DCCT) and described below
 - o Symptoms such as polyuria, polydipsia, nausea, or vomiting;
- o Serum ketones > 1.5 mmol/L or large/moderate urine ketones;
- 1016 o Either arterial blood pH <7.30 or venous pH <7.24 or serum bicarbonate (or CO₂) <15; and

1018	o Treatment provided in a health care facility	
1019 1020	• The event involved hyperosmolar hyperglycemic syndrome (HHS), as defined by the American Diabetes Association and described below	
1021	 Symptoms such as polyuria, polydipsia, nausea, or vomiting; 	
1022	 Plasma glucose levels are very elevated (typically > 600 mg/dL); 	
1023	 Plasma effective osmolarity is >320 mOsm/L; 	
1024	 Absence of significant ketones; and 	
1025	 Treatment provided in a health care facility 	
1026	 Hyperglycemia occurred that was associated with an ADE as defined in section 9.2.1 	
1027	Study device discontinued due to hyperglycemia	
1028 1029 1030 1031 1032 1033	When a hyperglycemia/ketotic event qualifies as an AE, or as an SAE as defined in section 9.2.1 a Hyperglycemia/DKA Form should be completed in addition to the Adverse Event Form. Events meeting DKA or HHS criteria should be considered to be serious adverse events with respect to reporting requirements. Hyperglycemia events not meeting criteria for DKA or HHS generally will not be considered as serious adverse events unless one of the SAE criteria in section 9.2.1 is met.	
1034 1035 1036	When a hyperglycemia/DKA event occurs during use of a study device, it generally will be considered to be unrelated to the device (per section 9.2.5) if the device functioned as intended and there does not appear to be a flaw in how the device is intended to function.	
1037 1038	9.2.5 Relationship of Adverse Event to Study Investigational Device or Study Procedure	

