1039 1040 1041 1042 1043 1044 1045 1046	by determining if there is a reasonable possibility that the adverse event may have been caused by the study device or study procedure. The Medical Monitor also will make this assessment, which may or may not agree with that of the site investigator. The Medical Monitor will have the final say in determining the causality as well as whether an event is classified as a serious adverse event and/or an unanticipated adverse device effect. Reporting requirements will be based on the Medical Monitor's assessment as the Sponsor's representative, with both the site	
1047 1048	Reporting requirements will be based on the Medical Monitor's assessment as the Sponsor's representative.	
1049 1050	To ensure consistency of adverse event causality assessments, investigators should apply the following general guideline when determining whether an adverse event is related:	
1051 1052 1053	Unrelated: The AE is clearly not related to a study device/procedure and a likely alternative etiology exists such as an underlying disease, environmental or toxic factors or other therapy.	
1054 1055 1056	Unlikely Related: The AE does not follow a reasonable temporal sequence during or after use of study device or a study procedure and a more likely alternative etiology exists such as an underlying disease, environmental or toxic factors, or other therapy.	

1057 1058 1059 1060 1061	Possibly Related: The AE occurred in a reasonable time during or after use of study device or a study procedure; but could be related to another factor such as an underlying disease, environmental or toxic factors, or other therapy; and there is a possible, though weak, scientific basis for establishing a causal association between the AE and the study drug/device.
1062 1063 1064 1065 1066	Probably Related: The AE occurred in a reasonable time during or after use of study device or a study procedure; is unlikely to be related to another factor such as an underlying disease, environmental or toxic factors, or other therapy; and there is a plausible, though not strong, scientific basis for establishing a causal association between the AE and the study drug/device.

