- Device malfunctions will be handled by the Sponsor or designee as described below. In the case
- of a CGM transmitter or sensor device malfunction, information will be forwarded to Dexcom by
- the site personnel, to be handled by their complaint management system.

1176

1140

1141

- Where an adverse event is suspected to be related only to the study provided insulin from Novo
- Nordisk, and does not result from a possible interaction with the investigational medical device,
- the investigator or the sponsor are encouraged to report the case to the FDA or competent
- authority. Where made aware of such case, the competent authority should apply the guidance
- provided in the Good Pharmacovigilance Practices Module VI with regard to the management of
- this type of safety report. While reporting the suspected adverse reaction, the relevant
- information regarding the CT (i.e. clinical trial number) or Study ID number must be included in
- the report.

1185 **9.5 Safety Oversight**

- The study Medical Monitor will review all adverse events and adverse device events that are
- reported during the study. SAEs typically will be reviewed within twenty-four (24) hours of
- reporting. Other AEs typically will be reviewed on a weekly basis.
- The Sponsor and Clinical Study Director will be informed of all cases of severe hypoglycemia
- and DKA or HSS and the Medical Monitor's assessment of relationship to the study device; and
- informed of all reported device issues. A Data and Safety Monitoring Board (DSMB) will
- provide safety oversight. The DSMB will be informed of all cases of severe hypoglycemia,
- DKA, and HHS irrespective of device relationship, all device-related SAEs, and all UADEs at
- the time that they occur during the study and will review compiled safety data at periodic
- intervals. The DSMB also will be informed of any ADEs not meeting criteria for a UADE if the
- 1196 Medical Monitor requests the DSMB review. The DSMB can request modifications to the study
- protocol or suspension or outright stoppage of the study if deemed necessary based on the
- totality of safety data available. Details regarding the DSMB's role will be documented in a
- separate DSMB charter.

1200

1201

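### Protocol 9.6.1 counts HHS toward the two-episode discontinuation rule but omits it from the condition for continuing after a single event

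*Protocol*

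**What the plan says.** Protocol 9.6.1 contains four event-specific rules for participants.

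- **Malfunction pause.** Closed-loop use is suspended after an unanticipated malfunction that caused severe hypoglycemia or DKA, "or a malfunction that could have led to severe hypoglycemia or DKA".
- **Two-episode rule.** Discontinuation follows "Two distinct episodes of DKA, HHS, or severe hypoglycemia as defined in sections 9.2.3" and 9.2.4.
- **Cause review.** "Each DKA or severe hypoglycemia event will be reviewed by the Medical Monitor with respect" to its cause and whether the study device was responsible.
- **Single-event condition.** "An additional requirement for continued study participation following a single DKA or severe hypoglycemia event" is that the investigator finds the event explainable, unlikely to recur and safe to continue after, and that the Medical Monitor concurs. The sentence after it, opening "If the Medical Monitor determines that the occurrence of the event indicates that it is not safe for the participant" to go on using the system, leads to discontinuation.

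Elsewhere HHS stands beside DKA. Protocol 9.2.4 says: "Events meeting DKA or HHS criteria should be considered to be serious adverse events". Under 9.5 the DSMB is told of severe hypoglycemia, "DKA, and HHS irrespective of device relationship, all device-related SAEs, and all UADEs at" the time they occur, and 9.6.2 repeats the immediate notice for all three acute events. HHS is also a key safety endpoint (11.4.4) and a described risk of hyperglycemia (1.5.1.4).

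**The concern.** The single-event condition sets the default after a first acute event. After DKA or severe hypoglycemia, the participant continues only if two parties agree. After HHS, the participant continues unless the investigator believes it is unsafe or another general ground for discontinuation applies. The Medical Monitor's discontinuation sentence does not close the gap, because the event it refers to is the DKA or severe hypoglycemia event of the sentence before.

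The protocol gives no reason for treating a first HHS event more lightly than a first DKA event. In an insulin-treated type 2 population HHS is one of the acute hyperglycemic emergencies that the safety plan is meant to cover. What is at stake is the protection of an individual participant before re-exposure to closed loop.

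**Working it through.** The main check is textual. The rules of 9.6.1 compare as follows.

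| Rule in 9.6.1 | Severe hypoglycemia | DKA | HHS |
|---|---|---|---|
| Malfunction pause | yes | yes | no |
| Two-episode discontinuation | yes | yes | yes |
| Medical Monitor cause review | yes | yes | no |
| Single-event condition and linked discontinuation sentence | yes | yes | no |

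HHS appears in one of the four. The next question is whether any other provision supplies the missing condition.

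- **Investigator bullet, 9.6.1.** It applies after any event, but it rests on one person's belief that continuing is unsafe. It asks for no finding that the event is explainable or unlikely to recur, and for no concurrence.
- **Medical Monitor review, 9.5.** It covers all reported adverse events, with serious ones typically seen within 24 hours of reporting. It is a review, and continuation does not wait for it. Under 9.4 the site's 24-hour deadline applies to serious events possibly related to a study device or to participation, and to unanticipated device effects; other reportable events have seven days. An HHS event judged unrelated could therefore reach the Medical Monitor days later. The same timing can apply to DKA, but there continuation depends on concurrence.
- **Causality, 9.2.5.** The Medical Monitor has the "final say in determining the causality as well as whether an event is classified" as serious or as an unanticipated device effect. That authority does not extend to continuation.
- **DSMB notice, 9.5 and 9.6.2.** It covers HHS, but it is not a participant-level condition.
- **Illness contact, 4.6.3.** Participants contact staff during significant illness so that a temporary stop of closed loop can be considered. This prompts a decision but requires no agreement before continuing.
- **SAP section 14.** Its event-review sentence names severe hypoglycemia and DKA, plus device-related serious events and unanticipated device effects. It does not name HHS.

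None of these makes the investigator's judgement plus Medical Monitor concurrence a condition for continuing after a first HHS event. Even if the Medical Monitor's discontinuation sentence is read broadly enough to include HHS, the two-party condition still does not apply.

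The two lesser omissions change little. Cause review of HHS is already covered by 9.5 and 9.2.5, and most under-delivery faults would trigger the malfunction pause because they could have led to DKA.

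**How many participants might be affected.** The inputs are 220 assigned to the automated system, about 200 completing, and 13 weeks of use (Protocol 11.3, SAP section 4).

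- Exposure with no dropout: 220 × 13/52 = 55 person-years.
- Exposure in completers only: 200 × 13/52 = 50 person-years.
- HHS rate: not given in the documents; assumed 0.1 to 2 per 100 person-years.
- Expected events: 0.001 × 50 = 0.05 at the low end; 0.02 × 55 = 1.1 at the high end.
- Chance of at least one (Poisson): 1 − exp(−0.05) = 4.9% to 1 − exp(−1.1) = 66.7%.

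**The case against.** The strongest reply is that the gap is narrow. A first HHS event is serious by rule and, by definition, was treated in a health care facility. The Medical Monitor reviews it, the sponsor and DSMB are told, and the investigator must stop a participant believed unsafe. The illness instruction in 4.6.3 would ordinarily prompt a decision on closed-loop use as well. All of this is correct, and it means that a first HHS event does not pass unnoticed. But these provisions are reviews, notices and prompts, and the protocol evidently thought something stronger was needed after a first DKA event, to which the same general safeguards also apply.

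A second reply is that the omission looks like an edit not carried through, since the change log records HHS being added to 9.5 and 9.6.2. That is plausible but cannot be shown from the documents. Whether deliberate or not, the rule as written is what sites will follow.

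A third reply is that the rate range is wide and assumed, so the 5% to 67% chance says little. That stands: the figures show only that cases would be few. The side items are also minor, and editing SAP section 14 would not by itself close the gap in 9.6.1.

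**Conclusion.** The concern holds. One rule is affected in substance: the single-event continuation condition with its linked Medical Monitor discontinuation sentence. As written, a participant has weaker protection before further closed-loop use after a first HHS event than after a first DKA event, and no reason is given.

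This conclusion rests on the text alone. The expected number of cases, 0.05 to 1.1, rests on the assumed HHS rate. Rarity limits how often the rule would be used, but not how a case should be handled when it occurs. Efficacy estimates, type I error and the reporting of HHS are unaffected. The change should be made because it concerns participant safety and costs little.

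**What to change.** In Protocol 9.6.1, extend the single-event condition to a single DKA, HHS or severe hypoglycemia event. The Medical Monitor discontinuation sentence that follows will then cover HHS without further editing.

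For consistency, add HHS to the cause-review and malfunction-pause sentences of 9.6.1. In SAP section 14, add HHS to the event-review sentence and align it with Protocol 9.5, which has the DSMB informed of each case. If HHS was left out on purpose, state the reason in 9.6.1.

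The cost is a few words in one protocol section and one SAP sentence. No visits are added, since 9.5 already has the Medical Monitor review every reported adverse event.
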